4.0 STAGING CRITERIA

Patients must have Stage I-III disease (AJCC 8TH EDITION, 2017).

5.0 ELIGIBILITY CRITERIA

Each of the criteria in the following section must be met in order for a participant to be considered eligible for registration in OPEN. Section 5 may be printed and used to by the site, but is not to be uploaded in RAVE (unless specially stated). For each criterion requiring test results and dates, please record this information on the Onstudy Form and submit via Medidata Rave® (see [Section 14.0](#)). Any potential eligibility issues should be addressed to the SWOG SDMC in Seattle at [name] or [contact] prior to registration. **NCI policy does not allow for waiver of any eligibility criterion (http://ctep.cancer.gov/protocolDevelopment/policies_deviations.htm).**

In calculating days of tests and measurements, the day a test or measurement is done is considered Day 0. Therefore, if a test is done on a Monday, the Monday 4 weeks later would be considered Day 28. This allows for efficient participant scheduling without exceeding the guidelines. **If Day 28 falls on a weekend or holiday, the limit may be extended to the next working day.**

5.1 Disease Related Criteria

- a. Patients must be diagnosed with Stage I-III solid tumor malignancy. Patients with only carcinoma in situ or with Stage IV disease are excluded.
- b. Patients must not have lymphoma, leukemia, or myeloma.
- c. Patients must not have primary liver cancer, known cirrhosis, or evidence of any malignancy that involves the liver.

5.2 Prior/Concurrent Therapy Criteria

- a. Patients must be planning to receive systemic anti-cancer therapy (either single agent or some combination of systemic cytotoxic therapy, systemic immunotherapy or systemic targeted therapy) for this solid tumor.
- b. Patients must not have been previously treated with the same anti-cancer therapy regimen that is now anticipated. The anti-cancer therapy does not have to be first-line therapy. Prior and/or concurrent radiotherapy is allowed.
- c. Patients must be registered \leq 28 days prior to the planned start date of anti-cancer therapy. If the patient has started systemic anti-cancer therapy, patient must be registered \leq 42 days after the initiation of first cycle of anti-cancer therapy.
- d. Patients who have received prior anti-cancer therapy must have discontinued all previous therapies (excluding planned anti-cancer therapy to occur in conjunction with this study) \geq 1 day prior to registration to this study.
- e. Patients must not have had any cancer therapy regimen that includes anti-CD20.

- f. Patients must not be receiving antiviral medications active against HBV, including: adefovir, entecavir, lamivudine, telbivudine, tenofovir disoproxil fumarate, tenofovir alafenamide (TAF), or any other FDA approved agents for the treatment of Hepatitis B. Patients who have previously received antiviral medication must not have required any antiviral medication active against HBV \geq 90 days prior to registration to this study.
- g. Patients must not have had hematopoietic stem cell transplantation therapy.
- h. Patients must not be taking or planning to take warfarin.
- i. Patients who will be treated with TAF must not be taking or planning to take oxcarbazepine, phenobarbital, phenytoin, rifabutin, rifampin, rifapentine, or St. John's Wort.

NOTE: Patients taking or planning to take the above listed concomitant medications may be treated with ETV or TDF (instead of TAF).

- j. Patients who will be treated with TAF and are concomitantly taking or plan to take carbamazepine must be given an increased dose of TAF (see Section 7.1) or alternatively be given ETV or TDF.

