3.0 DRUG INFORMATION

Investigator Brochures

For information regarding Investigator Brochures, please refer to SWOG Policy 15.

For this study, Tenofovir alafenamide (TAF), Tenofovir disoproxil Fumarate (TDF), and Entecavir (ETV), are commercially available; therefore, Investigator Brochures are not applicable to this drug. Information about commercial drugs is publicly available in the prescribing information and other resources.

Black Box Warnings: TAF, TDF, and ETV share a warning indicating severe acute exacerbations of HBV have been reported in HBV-infected patients who have discontinued anti-hepatitis B therapy. Hepatic function should be monitored closely in HBV-infected patients who discontinue therapy. Resumption of anti-hepatitis B therapy may be warranted, as clinically appropriate.

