5.3 Clinical/Laboratory Criteria

- a. Patients must have results for the following HBV tests done within 28 days prior to registration: HBsAg AND anti-HBc (total Ig or IgG, but not IgM only) AND anti-HBs. For the anti-HBs test, quantitative or qualitative (including "indeterminate") results are allowable. Refer to [Appendix 18.2](#) for viral status information.
- b. Patients must have tested positive for HBsAg or anti-HBc (total Ig, IgG, but not IgM) and must have baseline HBV DNA completed \leq 42 days prior to registration. See [Appendix 18.2](#) for viral status information.
- c. Complete blood count (CBC) must be completed \leq 28 days prior to registration. Results do not need to be in the institutional limits of normal.
- d. International Normalized Ratio (INR) must be completed \leq 28 days prior to registration. Results must \leq 1.2x institutional limits of normal.
- e. ALT and total bilirubin results must be obtained \leq 28 days prior to registration. ALT and total bilirubin must be $<$ 1.5x institutional ULN.
- f. Patients must have a baseline calculated creatinine clearance within 28 days prior to registration.

NOTE: Patients with reduced creatinine clearance may need a reduced dose of an antiviral drug (see details in Dose Modifications, [Section 8.2](#)).

- g. Patients must not have known current active hepatitis C infection (HCV). Active HCV is defined by a detectable HCV RNA level. Note: HCV testing is not required for eligibility.
- h. Patients must not have a history of human immunodeficiency (HIV) infection. Patients with unknown HIV status must have HIV testing completed \leq 365 days prior to registration.
- i. Patients must have Zubrod performance status of 0-2.

- j. Patients must be at least 18 years old.

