The primary analysis for each randomized experiment will be based on central, blinded review of adverse liver events among all randomized, eligible patients. A secondary examination in all randomized patients irrespective of their eligibility status will also be conducted under a fully intent-to-treat approach. To account for the potential for liver events to vary by cancer stage over and above what is reflected by the stratification variable (planned treatment type), in a secondary analysis, the investigators will adjust for cancer stage (adjuvant vs. advanced disease) as a covariate in the multivariable Cox regression model.

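### The second sentence of criterion 5.2f points its 90-day antiviral window in the wrong direction and should be reworded so the direction is explicit

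*Combined protocol and SAP*

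**What the plan says.** Section 5.2f has two sentences. The first deals with current use: "Patients must not be receiving antiviral medications active against HBV". The second deals with past use: "Patients who have previously received antiviral medication must not have required any antiviral medication active against HBV", and it closes with the window "HBV \geq 90 days prior to registration to this study" (the code is the greater-or-equal sign).

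Three other places decide how much weight the wording carries:

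- Section 5.0 requires every criterion to be met and adds that "NCI policy does not allow for waiver of any eligibility criterion". It also directs sites to take potential eligibility issues to the statistics and data management center before registration.
- Section 11.1 bases the primary analysis on centrally reviewed events "among all randomized, eligible patients". A secondary analysis takes all randomised patients whatever their eligibility.
- Section 14.1 says that patients whose documentation is too thin to determine eligibility will generally be deemed ineligible.

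No other section restates or corrects the 90-day window.

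**The concern.** The first sentence of 5.2f already removes anyone on an HBV antiviral at registration. The natural job of the second is to require a clear interval since the last use. As printed, it places the prohibition on the period 90 or more days back and says nothing about the 90 days just before registration.

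Two things are at stake. The first is who gets in: a patient with remote, finished treatment could be refused, while one with a short and very recent course could be registered.

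The second is what the outcomes mean. The protocol itself treats antiviral withdrawal as a cause of liver events. Section 3.0 carries the boxed warning that "severe acute exacerbations of HBV have been reported in HBV-infected patients who have discontinued anti-hepatitis B therapy"; Section 2.1 lists withdrawal of anti-HBV therapy among the causes of hepatitis flare; and Section 8.2 says that stopping may precipitate a flare. Section 10.2a measures reactivation against baseline HBV DNA. A recent short course could lower that baseline, and a later rebound would then meet the reactivation definition.

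**Working it through.** The plan gives no figure for this point. The check sets the wording side by side and then applies each reading to example histories.

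**Step 1. How Section 5 uses the signs.**

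- 5.2d, on earlier anti-cancer therapy: patients "must have discontinued all previous therapies" at least 1 day before registration. Here the greater-or-equal sign marks a time that far back or further. It goes with a positive requirement to have stopped, so the result is a washout.
- 5.3b: patients "must have baseline HBV DNA completed \leq 42 days prior to registration". Here the less-or-equal sign marks the window just before registration. 5.3c to 5.3e use it in the same way with 28 days.
- 5.2f uses the greater-or-equal sign of 5.2d, but with a negative requirement (not to have needed a drug). The combination reverses the meaning: the prohibited period becomes 90 or more days back.

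A fault in reading the PDF is unlikely, because the two signs are distinct and make sense in the neighbouring criteria.

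**Step 2. The two readings as rules** (day 0 is registration).

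- As printed: exclude if on an antiviral now, or if one was required at any time on or before day -90.
- Washout: exclude if on an antiviral now, or if one was required at any time from day -90 to day 0.

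**Step 3. Four assumed histories.**

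| History | As printed | Washout |
|---|---|---|
| A. Antiviral from day -200 to day -120 | excluded | admitted |
| B. Antiviral from day -30 to day -5 | admitted | excluded |
| C. Antiviral from day -200 to day -5 | excluded | excluded |
| D. Never treated | admitted | admitted |

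The readings give opposite answers for A and B and the same answer for C and D. The printed rule therefore admits a recent stopper only when all of that patient's antiviral use lies inside the last 90 days.

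**Step 4. Route to the endpoint.** Baseline HBV DNA may be up to 42 days old at registration (5.3b). In history B, a sample taken between day -30 and day -5 would be taken on treatment. Prior antiviral exposure is not a balancing factor in either cohort (Sections 6.1 and 6.2).

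**Step 5. Context for size.** This uses the design inputs of Section 11.1 and assumes 24 months of follow-up with no other dropout. The control hazard is -ln(0.90) = 0.1054, the experimental hazard is 0.30 × 0.1054 = 0.0316, and the competing death hazard is 0.223. The two-year cumulative incidence is h/(h + 0.223) × [1 - exp(-2(h + 0.223))].

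- Control: 0.1054/0.3284 × (1 - exp(-0.6567)) = 0.321 × 0.481 = 0.154; × 111 patients = 17.1 events.
- Experimental: 0.0316/0.2546 × (1 - exp(-0.5092)) = 0.124 × 0.399 = 0.0495; × 111 patients = 5.5 events.

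The total is about 22.6 primary events per cohort. This shows that events are few. It does not measure how many patients 5.2f affects, which the documents do not allow anyone to estimate.

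**The case against.** The strongest case on the other side is that this is a dropped word with an obvious meaning. The sentence opens by setting conditions under which previously treated patients may enter, and its verb, 'required', goes naturally with a duration. Put 'for' before the 90 days and it becomes a washout. Sites that are unsure have a route to ask before registration, and a ban on waivers does not forbid asking what a criterion means. Patients are randomised within cohort, so anyone misadmitted is not expected to fall mainly in one arm. Section 5.3e also requires ALT and total bilirubin below 1.5 times the upper limit within 28 days, which partly screens out a flare already under way.

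Much of this stands. The washout is probably what was meant, and the effect on the comparison between arms is limited. What does not stand is that the text can therefore be left alone. The missing word appears nowhere, the section's own usage points the other way, and the query route helps only a site that notices a problem.

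Three stronger readings are tempting, and the documents do not support them:

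- A reader might infer that anyone who stopped antivirals last week is eligible. History C shows otherwise: a long-term user who stopped recently is excluded under both rules.
- A reader might infer that the printed rule has in fact decided who was enrolled and analysed. Nothing in the documents shows how sites have applied it.
- A reader might infer that the treatment comparison is biased. Randomisation and the secondary analysis of all randomised patients argue against a systematic effect, and the endpoint definitions do not require events to be attributed to anti-cancer therapy.

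**Conclusion.** The point holds in limited form. Under Section 5's own usage, the second sentence of 5.2f excludes patients whose only HBV antiviral use was 90 or more days before registration, and it admits those whose entire course began and ended within the last 90 days. This goes beyond a clerical slip because the criterion cannot be waived and it helps define the primary analysis set. Two sites reading the line differently would contribute different patients.

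The harm is to consistency of enrolment, to the make-up of the primary analysis set and to the interpretation of early reactivation. The number of patients involved is unknown and may be small. No sample size, power or alpha figure changes. The conclusion assumes that the signs in 5.2f carry the same meaning as in 5.2d and 5.3b to 5.3e. The view that a washout was intended is an inference for the sponsor to confirm. The change should be made, but the design does not depend on it.

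**What to change.** 1. The sponsor should confirm the intended window and amend the second sentence of 5.2f so that its direction cannot be misread. If a washout is intended, one form would be that no HBV-active antiviral was required within the 90 days before registration. The verb 'required' should stay unless the sponsor also means to change it: 'received' would be a separate, substantive edit.
2. Check registered patients with prior antiviral exposure against the corrected wording, without reference to assigned arm or outcome. State before the primary analysis whether patients registered under the printed wording count as eligible. This check cannot recover patients who were refused under the literal reading, because they were never registered.

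The cost is a one-line amendment and a review of recorded prior antiviral use. The documents do not show whether the Onstudy Form captures the dates of such use; if it does not, a short query to sites would be needed.

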5.3 Clinical/Laboratory Criteria

- a. Patients must have results for the following HBV tests done within 28 days prior to registration: HBsAg AND anti-HBc (total Ig or IgG, but not IgM only) AND anti-HBs. For the anti-HBs test, quantitative or qualitative (including "indeterminate") results are allowable. Refer to [Appendix 18.2](#) for viral status information.
- b. Patients must have tested positive for HBsAg or anti-HBc (total Ig, IgG, but not IgM) and must have baseline HBV DNA completed \leq 42 days prior to registration. See [Appendix 18.2](#) for viral status information.
- c. Complete blood count (CBC) must be completed \leq 28 days prior to registration. Results do not need to be in the institutional limits of normal.
- d. International Normalized Ratio (INR) must be completed \leq 28 days prior to registration. Results must \leq 1.2x institutional limits of normal.
- e. ALT and total bilirubin results must be obtained \leq 28 days prior to registration. ALT and total bilirubin must be $<$ 1.5x institutional ULN.
- f. Patients must have a baseline calculated creatinine clearance within 28 days prior to registration.

NOTE: Patients with reduced creatinine clearance may need a reduced dose of an antiviral drug (see details in Dose Modifications, [Section 8.2](#)).

- g. Patients must not have known current active hepatitis C infection (HCV). Active HCV is defined by a detectable HCV RNA level. Note: HCV testing is not required for eligibility.
- h. Patients must not have a history of human immunodeficiency (HIV) infection. Patients with unknown HIV status must have HIV testing completed \leq 365 days prior to registration.
- i. Patients must have Zubrod performance status of 0-2.

- j. Patients must be at least 18 years old.
- k. Patients must not be pregnant or nursing, as the safety of the study drug in pregnant and nursing women has not been established. Women/men of reproductive potential must have agreed to use an effective contraceptive method. A woman is considered to be of "reproductive potential" if she has had menses at any time in the preceding 12 consecutive months. In addition to routine contraceptive methods, "effective contraception" also includes heterosexual celibacy and surgery intended to prevent pregnancy (or with a side-effect of pregnancy prevention) defined as a hysterectomy, bilateral oophorectomy or bilateral tubal ligation. However, if at any point a previously celibate patient chooses to become heterosexually active during the time period for use of contraceptive measures outlined in the protocol, he/she is responsible for beginning contraceptive measures.

5.4 Specimen Submission Criteria

- a. Patients must have specimens collected for submission as outlined in [Section 15.1](#).
- b. Patients must be offered the opportunity to participate in optional translational medicine studies as outlined in [Section 15.2](#).

5.5 Regulatory Criteria

- a. Patients with impaired decision-making capacity are eligible as long as their neurological or psychological condition does not preclude their safe participation in the study (e.g., tracking pill consumption and reporting adverse events to the investigator).
- b. Patients may have concurrent participation in other clinical trials that entail cytotoxic, immunotherapy, targeted therapy; surgical treatment; radiotherapy treatment; or any combination thereof.
- c. Patients **must** be informed of the investigational nature of this study and must sign and give written informed consent in accordance with institutional and federal guidelines.
- d. As a part of the OPEN registration process (see [Section 13.3](#) for OPEN access instructions) the treating institution's identity is provided in order to ensure that the current (within 365 days) date of institutional review board approval for this study has been entered in the system.

6.0 STRATIFICATION FACTORS

6.1 Cohort 1: Chronic HBV cohort

Patients with chronic HBV will be randomized between Arm 1 (prophylactic anti-HBV therapy) or Arm 2 (upon indication anti-HBV therapy) using a dynamic allocation scheme. Patient randomization to the two treatment arms will be balanced on:

- Planned cancer therapy type: cytotoxic (with or without immunotherapy or targeted therapy) vs. immunotherapy alone vs. targeted therapy alone vs. immunotherapy and targeted therapy.

6.2 Cohort 2: Past HBV cohort

Patients with past HBV will be randomized between or Arm 3 (upon indication anti-HBV therapy) or Arm 4 (usual care) using a dynamic allocation scheme. Patient randomization to the two treatment arms will be balanced on:

- Planned cancer therapy type: cytotoxic (with or without immunotherapy or targeted therapy) vs. immunotherapy alone vs. targeted therapy alone vs. immunotherapy and targeted therapy.
- Anti-HBV status: positive vs. negative.

7.0 TREATMENT PLAN

For treatment or dose modification questions, please contact [name]., M.P.H., [contact], E-mail: [contact] or [name]., [contact] or E-mail: [contact]. For dosing principles or questions, please consult the SWOG Policy #38 "Dosing Principles for Patients on Clinical Trials" at <http://swog.org> (then click on "Policies & Procedures" under the "About" menu and choose Policy 38).

7.1 General Treatment Information

a. Concomitant Medications

Concomitant medications must be assessed prior to initiation of antiviral therapy in Arm 1 (prophylaxis) or if initiated if HBV reactivation occurs (upon indication) in Arms 2 and 3.

Refer to the current FDA-approved package insert for the most comprehensive and up to date information on concomitant medications.

TAF: Concomitant administration of oxcarbazepine, phenobarbital, phenytoin, rifabutin, rifampin, rifapentine, or St. John's Wort is not recommended. If co-administered with carbamazepine, TAF dose should be increased to two tablets once daily. Alternatively, if the above medications cannot be stopped, then study patients may take TDF or ETV.

TDF: none

ETV: none

If possible, avoid use of warfarin. If medically necessary, warfarin may be used during protocol participation after enrollment. For patients who need to take warfarin, monitor INR per [Section 9](#). If the patient has an INR increase, the treating investigator should review to determine if the cause is due to warfarin, study treatment, or acute liver injury. If INR increase is due to acute liver injury, and the increased INR is accompanied by AST, ALT, and bilirubin increase, evaluate the cause per [Section 9](#). Document this determination in the patient's chart.

b. Guidance for Offsite and Virtual Options during the Conduct of the Trial

1. **Laboratory assessments and specimen collections**: All laboratory assessments and specimen collections must be completed at protocol-specified timepoints (see [Section 9.0](#)).
2. **Conducting labs at an offsite facility**: In order to provide participating sites flexibility in treating patients, it is the intent of the **S1614** protocol to

allow for laboratory assessments to be drawn and resulted by local healthcare providers (with appropriate oversight by the Responsible Investigator [local treating investigator]), where administration of the assessment at an off-site facility is in the best interest of the patient and provides for continuity of patient care. Utilization of offsite / local healthcare resources for conduct of patient's laboratory assessments must be documented including procedures for oversight (by the Responsible Investigator) of assessments performed offsite.

3. **Assessments via virtual methods:** The following assessments may be performed by a research RN, CRA, Advanced Practice Provider (APP), or physician. The assessments may be conducted virtually via phone or videoconferencing:

- HBV Assessment
 - Obtain the HBV assessment in person, over the phone, or videoconference with the patient and document on the HBV Assessment Form ([Section 14.4](#))
- Toxicity Notation (AE Assessment)
 - Obtain the AE assessment in person, over the phone, or videoconference with the patient and document on the Anti-Viral Adverse Event Form ([Section 14.4](#))
- Review of Intake Calendar
 - Patient may be instructed to submit Intake Calendar electronically per site institutional standards.

